3.4 Primary endpoint/outcome

Change in AIS motor score at 6 months versus baseline (Δ AMS).

3.5 Secondary endpoints/outcomes

- Change in AIS sensory score (light touch) at 6 months compared with baseline (all patients)
- Change in AIS sensory score (pin prick) at 6 months compared with baseline (all patients)
- Change in AIS grade at 6 months compared with baseline (all patients)
- CUE-Q (upper limb function) at 6 months (all patients)
- Grip strength (hand function) at 6 months (all patients)
- WISCI-II (walking ability) at 6 months (all patients)
- SCIM-III (self-care and daily living) at 6 months (all patients)
- SF-36 at 6 and 12 months (all patients)
- Number of re-operations required on the spine within 12 months (all patients)
- Total length of hospital stay (Stay in MTC, stay in spinal injury unit, other hospital admissions) (all patients)
- Surgical complications and adverse events – recorded postoperatively and at follow-up visits

- OS – time from randomisation to death or end of follow-up (1 year) (all patients)
- MRI at 6 months: Spinal deformity (Cobb angle between the superior endplate of C2 to the inferior endplate of C7) (all patients)
- MRI at 2 weeks: Length of cord compression (no CSF around the cord in mid-sagittal MRI), Size of pseudomeningocele
- MRI at 6 months: Length of cord tether, Length of cord syrinx (all patients), Size of pseudomeningocele
- Pressure monitoring at injury site: Mean daily ISP, Mean daily SCPP (mechanistic study patients)
- MD monitoring at injury site: Mean daily metabolites (glucose, lactate, pyruvate, LPR, glutamate, glycerol), Mean daily cytokines/chemokines (GRO α , IL1 α , IL1 β , IL4, IL8, IL10, IP10, MCP1, MIP1 α , MIP1 β , or others) (mechanistic study patients)

Objective	Outcome Measure	Timepoint(s) of evaluation of this outcome measure
PRIMARY: To determine if bony + dural decompression improves motor score	Change in AIS motor score	6 months minus baseline
SECONDARY 1: To determine if bony + dural decompression improves neurological outcome	Change in AIS sensory score (light touch)	6 months minus baseline
	Change in AIS sensory score (pin prick)	6 months minus baseline
	Change in AIS grade	6 months minus baseline
SECONDARY 2: To determine if bony + dural decompression improves functional outcomes	CUE-Q	6 months
	Grip strength	6 months
	WISCI-II	6 months
	SCIM-III	6 months
SECONDARY 3: To determine if bony + dural decompression improves quality of life	SF-36	6, 12 months
SECONDARY 4: To determine if bony + dural decompression improves MRI features, improves cord perfusion and reduces cord inflammation at the injury site.	MRI length of cord compression (no CSF around the cord in mid-sagittal MRI)	2 weeks
	MRI size of pseudomeningocele (cranio-caudal, antero-posterior, medio-lateral lengths, and estimated volume)	2 weeks, 6 months
	MRI Length of cord tether in mid-sagittal MRI	6 months
	MRI Mid sagittal length of cord syrinx	6 months
	Pressure monitoring at injury site: mean daily ISP (mechanistic study patients only)	Up to 5 days after surgery
	Pressure monitoring at injury site: mean daily SCPP (mechanistic study patients only)	Up to 5 days after surgery
	MD monitoring at injury site: mean daily glucose, lactate, pyruvate, LPR, glutamate, glycerol (mechanistic study patients only)	Up to 5 days after surgery

	MD monitoring at injury site: mean daily cytokines (GRO α , IL1 α , IL1 β , IL4, IL8, IL10, IP10, MCP1, MIP1 α , MIP1 β) (mechanistic study patients only)	Up to 5 days after surgery
SECONDARY 5: To determine if bony + dural decompression is safe.	Number of re-operations on spine	12 months
	Total hospital stay	12 months
	Complications and adverse events	12 months
	Overall survival (OS): from randomisation to death or end of follow-up	12 months
	MRI Spinal deformity: Cobb angle between superior C2 and inferior C7 endplates	6 months

4 TRIAL DESIGN

DISCUS is a randomised, controlled multi-centre trial with two trial arms: 1) surgical decompression including laminectomy (standard of care, control), and 2) surgical decompression including laminectomy + duroplasty. It is a superiority trial, i.e. it aims to show that the trial arm that includes duroplasty improves outcome compared to the control arm. It has a parallel group design i.e. participants will be randomised 1:1 to receive only one of the two trial treatments, i.e. standard of care with laminectomy OR standard of care with laminectomy + duroplasty. The trial will be double-blind i.e. neither the patient nor the assessor of the primary outcome measure at 6 months will know the trial treatment. The assessor at 6 months will be a different hospital from the MTC where the surgery took place and they will not have easy access to the MTC clinical records or operation note.

MECHANISTIC STUDY: A subset of patients, at least N = 50 (at least 25 in each arm), will undergo monitoring from the injury site of ISP + SCPP and/or MD, for up to 5 days after surgery. All centres must ensure that patients who consent and are included in the mechanistic sub-study must first consent to participation in the main trial.

INTEGRATED QUINTET RECRUITMENT INTERVENTION (QRI): this is designed to optimise recruitment and informed consent and is embedded during the first two years of recruitment (months 7 – 30).

- National Spinal Injuries Centre, Stoke Mandeville Hospital, Aylesbury;
- Welsh Spinal Cord Injury Rehabilitation Centre, Cardiff;
- Spinal Cord Injury Unit for Northern Ireland, Belfast

INTERNATIONAL CENTRES: DISCUS started as a UK study, but expanded to include international centres. It is anticipated that international centres will contribute to the recruitment for DISCUS <50 % of the total number of patients and will be required to seek their own funding to support recruitment. International centres will adopt the DISCUS protocols of patient assessment, follow-up,

investigations, outcomes etc. and randomise via the same process as the UK centres. These international centres will be sponsored by Gemeinnützige Salzburger Landeskliniken Betriebsgesellschaft mbH (SALK), [name]. Changed regulations due to Brexit will be integrated into DISCUS as they become available including UK and EU data sharing, processing and access agreements.

6 PARTICIPANT ELIGIBILITY CRITERIA

6.1 Inclusion criteria

1. Age ≥16 years
2. Severe cervical (C2 – T1) TSCI (AIS grade A–C)
3. Deemed to require and be suitable for surgery that includes laminectomy by local surgeon
4. Surgery within 72 hours of TSCI
5. Able to provide informed consent (except in emergency) or consultee declaration or proxy consent.

6.2 Exclusion criteria

1. Probable dural tear due to TSCI
2. Life-limiting or rehabilitation-restricting co-morbidities
3. Thoracic or lumbar TSCI
4. Other CNS disease

7 TRIAL PROCEDURES

7.1 Recruitment

7.1.1 Participant identification

All patients admitted to the Emergency department, Neurosurgical ward or Neurosurgical Intensive Care Unit or ICU with a TSCI will be screened for eligibility to include into the DISCUS trial based on clinical presentation. A member of the direct clinical care team will assess potential eligibility of patients based on the inclusion/exclusion criteria in Section 6.1 and 6.2.

7.1.2 Screening

SCREENING ASSESSMENT: Patients are admitted as emergencies to the Emergency Department initially, then Neurosurgical Unit or ICU where initial investigations, management and assessments are made. A baseline ISNCSCI AIS assessment should be standard of care and will be performed on admission and used to assess the severity of injury as AIS grade (grades A – C eligible). Trial specific assessments will only be conducted after participants have given written informed consent (except in emergency) or PLR consent given. Medical history which would preclude eligibility will be obtained from the clinical team, the patient case notes or after discussion with the patient (or patient's representative – if available).

PARTICIPANT RANDOMISATION: Patients who agree to take part will be enrolled to DISCUS +/- the mechanistic study based on their clinical presentation. A unique randomisation number will be allocated to each patient.

After randomisation, a letter will be sent to the patient's GP regarding the DISCUS trial, informing the GP about the patient's participation but not allocation. The rehabilitation centre (Spinal Injuries Unit) that receives the patient after discharge from the MTC will also be informed about the patient's participation into the DISCUS trial. A pseudonymised record of all patients screened, identified as

eligible, approached and invited to take part in the trial will be kept using the SEAR framework [Wilson et al., 2018]. This will be entered electronically onto a screening log}. This information will be used to identify any barriers to recruitment and allow improvement measures to be identified and implemented in a timely manner (See section on integrated qualitative research below)

7.2 Consent

RESPONSIBILITY FOR CONSENT: The local Principal Investigator (PI) retains overall responsibility for the conduct of research at their site, this includes the taking of informed consent of participants at their site. They must ensure that any health professional delegated responsibility to screen, discuss the study with patients (or patient legal representatives) and obtain informed consent is duly authorised, trained and competent to participate according to the ethically approved protocol, principles of Good Clinical Practice (GCP) and Declaration of Helsinki. Health professionals involved in screening and discussing the study will typically be from neurosurgery or ICU and medically qualified, including consultants, specialist trainees, research or clinical fellows. The PI takes responsibility for ensuring that all vulnerable participants are protected and participate voluntarily in an environment free from coercion or undue influence. Each PI also takes responsibility for ensuring that all local GCP certificates are up to date.

TIMING OF CONSENT: Informed consent must be obtained prior to the participant undergoing procedures that are specifically for the purposes of the trial. Consent must be taken prior to study randomisation. As much time as possible (at least 2 hours) will be allowed between explaining the study, that includes providing the PIS, and obtaining the consent. This timeframe may be required to enable the person giving consent to digest the information provided before reaching a decision whether to agree to participate.

WITHDRAWAL OF CONSENT: The right of a participant to refuse participation without giving reasons must be respected. The participant must remain free to withdraw at any time from the trial without giving reasons and without prejudicing his/her further treatment and must be provided with a contact point where he/she may obtain further information about the trial. All participants will continue to be followed up as per routine NHS standard of care. Withdrawn participants will be asked whether the data acquired up to the point of withdrawal can be retained. The reason for withdrawal will be recorded in the participant's medical records and in the Care Report Form (CRF). Any intention to utilise such data should be outlined in the consent literature. Where a participant is required to re-consent or new information is required to be provided to a participant it is the responsibility of the PI to ensure this is done in a timely manner. If a patient decides to withdraw from the DISCUS trial, their GP will be notified, and any data or samples collected will be retained unless the patient wishes for them to be destroyed.

CONSENT OBTAINED FROM PATIENT: Where potential patients fulfil the eligibility criteria, they will be approached by a member of the research or clinical team who will provide the patient information sheet, and where facilities and time allow the patient information video and answer any questions the patient may have. Wherever possible informed consent will be obtained from the patient. If the patient verbally consents to participate but is unable to sign because of hand weakness as a result of the TSCI, then the form will be signed by an independent healthcare professional (IHP) defined as a witness that the patient has consented. This witness is not the person taking consent. This will be documented in the patient's notes.

NON-ENGLISH SPEAKERS: We confirm that DISCUS aims to recruit non-English speakers as per the Equality, Diversity and Human Rights Act. This will be achieved using an interpreter, who is either a member of staff, or the professional telephone or face-to-face Interpreter and Translation service (Language Line) available to each NHS centre.

CONSENT OR CONSULTATION WITH PERSON OTHER THAN THE PATIENT: DISCUS involves patients who have suffered serious cervical TSCI. Some patients may have difficulty breathing thus requiring sedation and ventilation. Most patients will have capacity to provide informed consent, but some patients may have impairment in their level of consciousness from the sedative drugs. In this emergency situation, these sedated patients may not be able to understand the information relevant to the decision, retain the information, use or weigh the information or communicate his or her decision (by any means). In addition, the surgery has to be performed within 72 hours after injury.

ENGLAND AND WALES: DISCUS is classified as intrusive research. The recruitment of sedated patients complies with the Mental Capacity Act 2005:

- The research is connected with an impairing condition affecting the participant (TSCI) and tests a novel treatment (expansion duroplasty).
- Research of equal effectiveness could not be carried out if confined to TSCI participants with capacity because we will not be able to recruit enough patients to obtain meaningful results.
- The RCT has the potential to benefit the participant without imposing a disproportionate burden. The mechanistic study will provide knowledge of the causes of, or treatment or care of others with the same condition, involves negligible risk to the participant and does not interfere significantly with their freedom of action or privacy, and is not unduly invasive or restrictive, based on our experience to date with more than 80 TSCI patients from the ISCoPE study.
- We have arrangements in place to comply with section 32 (consulting carers) and section 33 (additional safeguards including the freedom to withdraw and respect for advanced statements), see Table below.

NORTHERN IRELAND: The Mental Capacity Act (Northern Ireland) 2016 is closely aligned with Mental Capacity Act 2005, which applies in England and Wales.

SCOTLAND: DISCUS complies with Section 51 of the Adults with Incapacity (Scotland) Act 2000:

- Research of a similar nature cannot be carried out on an adult who is capable in relation to such a decision because we will not be able to recruit enough conscious patients to obtain meaningful results.
- The purpose of the research is to obtain knowledge of the treatment or care of the adult's TSCI.
- The RCT and the mechanistic study will contribute through significant improvement in the scientific understanding of the adult's incapacity (TSCI) to the attainment of real and direct benefit to the adult or to other persons having the same incapacity.
- The adult does not indicate unwillingness to participate in the research.
- DISCUS (the RCT and mechanistic study) entails only a minimal foreseeable risk to the adult.
- The research imposes no discomfort, or only minimal discomfort, on the adult.
- Consent will be obtained from any guardian or welfare attorney who has power to consent to the adult's participation in research or, where there is no such guardian or welfare attorney, from the adult's nearest relative, see Table below.

ENGLAND, WALES	SCOTLAND

1. Personal Consultee
 
a) A person engaged in caring for the participant (not professionally or for payment) or is interested in his/her welfare, and b) Is prepared to be consulted.
	
1. Nearest Relative/Guardian or Welfare Attorney
 
1A. A guardian or welfare attorney who has power to consent to the adult's participation in research. 1B. If there is no such person, the adult's nearest relative as defined in 87(1) of the Adults with Incapacity Act 2000.

2. Nominated Consultee
 
If no appropriate person can be identified who is willing to act as a personal consultee, we will consult a "nominated consultee", i.e. a person independent of DISCUS appointed in accordance with the Department of Health's guidance.
	
2. Welfare Attorney
 
A person not connected with the conduct of the trial who is: a) the doctor primarily responsible for the adult's medical treatment, or b) a person nominated by the relevant health care provider.
 
A professional legal representative will be approached if it is not reasonably practicable to contact 1A or 1B before the decision to enter the adult into DISCUS is made. Informed consent must be given before the subject is entered into DISCUS.

1. Where patients are unable to provide consent because of sedative medication, a consultee will be sought (England and Wales) or a nearest relative/guardian or welfare attorney (Scotland). If this person is available in the hospital, is contactable, or is due to visit the patient within a reasonable timescale, then they will be provided with information about the trial and asked if they will provide written consent for the patient. This will be documented in the patient's notes.
2. Situations may arise in which the patient is sedated and there is no personal consultee (England and Wales) or nearest relative/guardian or welfare attorney (Scotland) or where this person is not contactable or able to visit the hospital at short-enough notice to be able to enrol the patient in a timely manner. In such cases we advocate enrolment would be possible with written agreement from a nominated consultee (England and Wales) or a welfare attorney (Scotland) as defined in the Table. This will be documented in the patient's notes.

In emergency situations, a patient unable to consent for themselves may still be recruited into DISCUS without prior advice from a consultee. In England and Wales, the law allows patients who are otherwise eligible for DISCUS but not able to consent for themselves to be recruited without prior advice from a consultee, in emergency situations if the local team decide that:

- treatment needs to be given urgently
- it is not reasonably practicable to seek advice from a consultee
- the procedure is approved by a NHS Research Ethics Committee
- a consultee is consulted as soon as possible to seek advice on the participant's likely views and feelings.

In emergency situations, a registrar/consultant or equivalent neurosurgeon who does not have GCP certificate may obtain consent or consultee advice for DISCUS. It should be noted that there is no legal requirement for studies which are not clinical trials of investigational medicinal products to be conducted in accordance with the conditions and principles of GCP. However, it is still important that such research is always conducted in a manner that provides public assurance that the rights, safety

and wellbeing of research participants are protected and that research data are reliable. Members of the research team in such studies are expected to be qualified by education, training or experience but should not be required or expected to undertake GCP training.

RETROSPECTIVE CONSENT: Patients who entered DISCUS via proxy consent and who regain capacity whilst in hospital will be informed about the trial and retrospective consent to continue participation will be sought from them. If at any stage either the consultee or nearest relative/guardian or welfare attorney or the patient chooses to withhold consent, then the patient will be withdrawn from the trial. Any advance statement by the participant will be respected.

A PERSON NOT CONNECTED WITH THE CONDUCT OF THE TRIAL: For the purposes of the DISCUS trial, the following people are excluded from providing consent:

- a) A person who undertakes activities connected with the management of the trial;
- c) An investigator of the trial or;
- d) A health care professional who is a member of the investigators delegated team for the purposes of the trial.

INFORMED CONSENT FORM: The Informed Consent/Consultee declaration forms must be approved by the REC and must be in compliance with GCP, local regulatory requirements and legal requirements. The investigator or designee must ensure that each trial participant, or his/her legally acceptable representative, is fully informed about the nature and objectives of the trial and possible risks associated with their participation. The Informed Consent/Consultee declaration form used for this trial and any change made during the course of this trial, must be prospectively approved by the REC. The investigator will retain the original of each participant signed informed consent form. QRI is an optional part of the study; a consent form and PIS (different from the ones used for the RCT or the mechanistic study) will be used for QRI and will mention that the patient may be contacted by QRI researchers (see 7.2.1).

NEW INFORMATION: Any new information which becomes available, which might affect the participant's willingness to continue participating in the trial will be communicated to the participant as soon as possible, verbally if the participant is in hospital, or by post/email if they have been discharged. We do not anticipate any such information.

7.2.1 Additional consent provisions for collection and use of participant data and biological specimens in ancillary studies, if applicable

CONSENT FOR MONITORING FROM INJURY SITE: Patients who, in addition to the main RCT, are also recruited into the mechanistic study (i.e. insertion of probes to monitor from the injury site) will receive additional information regarding these monitoring studies including on the PIS. The signed consent form will require the consenting person to indicate whether the patient has consented only for the clinical study or for both the clinical study plus injury site monitoring study. MD specimens will be analysed on site for standard metabolites (glucose, lactate, pyruvate, glutamate, glycerol). These samples will be stored on site and periodically shipped (anonymously) to [name] at City St. George's for further assay of cytokines. MD samples are not human tissue as they are fluid collected through a 20 kDa MD dialysis membrane; the MD samples thus only contain fluid molecules <20 kDa in size.

CONSENT FOR QRI: The QRI involves inviting patients to take part in an audio-recording of their recruitment discussion and/or take part in an interview about their experience of being invited to join the study. Prior to discussion of DISCUS, written consent may be sought from patients/their legal representative to audio-record the recruitment discussion and/or take part in an interview with the QRI

researcher as part of the integrated qualitative research. Patients will be able to consent to the audio recording and/or interview and decline participation in DISCUS or vice versa, decline the audio recording and/or interview but consent to participation in DISCUS. A separate consent form will record consent to take part in the integrated qualitative research.

7.3 The randomisation scheme

Once the patient has been identified as eligible, invited to take part and given their consent (except in emergency)/had consent provided by consultee or nearest relative/guardian or welfare attorney, participants will be randomised by a member of the research team on the site delegation log authorised to do so. We recommend that randomisation is done just before the surgery to minimise patient withdrawal post-randomisation.

Participants will be randomly allocated to the treatment options using a web based secure randomisation system (RRAMP) provided by the Oxford Clinical Trials Research Unit (OCTRUE). Randomisation allocation will be implemented using a minimisation algorithm with the following minimisation factors:

- 1) Age group (<40, 40-60, >60 years)
- 2) Country (England, Wales, Scotland, Northern Ireland, plus others if International centres participate and randomise patients to the study).

The minimisation algorithm will be seeded with a number of allocations and a non-deterministic probabilistic element will be introduced in order to prevent predictability of the treatment allocation.

The participant's identifiable information – participant initials, sex, age, hospital number (medical record number), centre, will be recorded on the REDCap screening form which feeds into the randomisation form for randomisation on RRAMP, and will be uploaded to an encrypted, separate database at the University of Oxford. Name, date of birth, email, address, telephone number will be recorded in contact details for patient reported outcome collection by central team. These and the NHS number (CHI number in Scotland) collected will facilitate identification of patients at rehabilitation centres for follow up. Hospital number (or medical record number (MRN)) facilitates the identification of an emergency setting patient. Ethnicity will be collected at baseline. This information will be encrypted in REDCap with access of only trial administration at SITU.

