10.3.2 Primary outcome analysis

The primary analysis will be performed according to the intention-to-treat principle and will be analysed at a 2-sided 5% significance level. The primary outcome, change in AMS score from baseline to 6 months, will be analysed using a generalised estimating equation (GEE) model or mixed model for repeating measures (MMRM) model (depending on the distribution of the primary outcome),

adjusted for randomised treatment and baseline AIS grade. Minimisation factors (age group, country) will be adjusted for as fixed effects. A secondary analysis will be performed adjusting for other important, pre-specified prognostic factors. The mean score and SD will be plotted at each time-point as a visual representation and will be summarised at baseline, 3 months and 6 months.

The AIS ISNCSCI assessment involves systematically completing the AIS form and, therefore, we do not anticipate missing values. Any missing date for the primary outcome (AMS) will be reviewed on a case-by-case basis by an independent clinician who is blinded to the treatment the patient received. AIS grade A or B patients have 0 motor score below the injury by definition and will thus be included in the primary analysis, whereas an AIS grade C patient cannot have missing motor scores and therefore, in the possible but unlikely scenario where values are missing, the AIS will be independently reviewed.

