10.3.3 Secondary outcome analysis

MMRM will be used to evaluate difference over time by treatment group in HRQoL outcomes. MMRM models will be adjusted for minimisation factors, treatment, baseline score, visit and a treatment by visit interaction as fixed effects, with patient included as a random effect. Differences between treatment groups will be reported as mean differences with 95% confidence intervals. Absolute and percentage changes in HRQoL outcomes from baseline assessment will be displayed graphically. HRQoL forms that are returned partially complete will be analysed according to the scoring instructions for each questionnaire.

Binary outcomes will be assessed using chi-squared tests and logistic regression analyses, adjusting for baseline and minimisation factors. Normality will be assessed for continuous outcome measures and differences between treatment arms will be assessed using a t-test or Mann-Whitney U test and presented as mean differences with 95% confidence intervals or median differences with interquartile range. Linear regression or GEE models will be used to adjust for baseline, minimisation and other important prognostic factors.

Survival analysis methods will also be used to compare differences between the treatment groups for overall survival (OS). Time to OS will be displayed using Kaplan-Meier plots.

Absolute (death rates at 12 months) and relative differences (hazard ratios) will be reported together with 95% confidence intervals.

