10.4 Subgroup analyses

Exploratory sub-group analyses will assess the impact of the minimisation factors under the treatment effect. Planned subgroup analyses will be specified in the SAP.

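### Section 10.3.3 leaves baseline AIS grade out of the quality-of-life and logistic models, and because no baseline SF-36 is collected, quality of life as written has no adjustment for injury severity

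*Protocol*

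**What the plan says.** Protocol 7.3 states: "Randomisation allocation will be implemented using a minimisation algorithm with the following minimisation factors". It gives two: "Age group (<40, 40-60, >60 years") and "Country (England, Wales, Scotland, Northern Ireland, plus others if International centres participate and randomise patients to the study"). AIS grade is not among them, although 6.1 makes grades A to C an inclusion criterion and 7.1.2 has the grade assessed on admission.

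Protocol 10.3.2 specifies the primary model as "adjusted for randomised treatment and baseline AIS grade", and adds: "Minimisation factors (age group, country) will be adjusted for as fixed effects".

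Protocol 10.3.3 specifies the secondary models. For HRQoL: "MMRM models will be adjusted for minimisation factors, treatment, baseline score, visit and a treatment by visit interaction as fixed effects". For binary outcomes: "Binary outcomes will be assessed using chi-squared tests and logistic regression analyses, adjusting for baseline and minimisation factors". Other continuous outcomes get a linear or GEE regression that may also include further prognostic factors.

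Table 1 in 7.7 and the schedule in Appendix 2 place SF-36 at 6 and 12 months only. The baseline row of Table 1 holds patient characteristics, AIS, MRI and CT.

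**The concern.** The primary model treats injury severity as prognostic. The allocation does not balance it, and two of the secondary model specifications do not name it.

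The HRQoL model is the clearer case. Its covariate list would normally pick up severity indirectly through the baseline score, but no SF-36 is taken at baseline and, in an emergency population, none is planned. What remains is age group, country, visit and treatment. Nothing in that model reflects how severe the injury was.

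At stake are precision and protection against a chance difference between arms in outcomes on which the protocol leans. Section 10.1 uses HRQoL to show that any functional improvement reaches the patient.

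**Working it through.** **1. Covariates side by side**

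| Analysis | Stated covariates | AIS grade named? |
|---|---|---|
| Primary (10.3.2) | treatment, AIS grade, age group, country | yes |
| HRQoL mixed model (10.3.3) | minimisation factors, treatment, baseline score, visit, treatment by visit | no, and the baseline score is not collected |
| Logistic models (10.3.3) | baseline, minimisation factors | not by name |
| Other continuous (10.3.3) | baseline, minimisation, other prognostic factors | allowed |

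**2. The plan's own sample size**

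Inputs from 10.1: difference 28 − 17 = 11, SD 25, two-sided 5%, power 85%, loss 15%. The two-sample t-test needs 93.7 per arm, so 94, or 188 in total. 188 / 0.85 = 221.2, so 222. The stated figure is reproduced and is not in dispute. Evaluable per arm at 222: 222 × 0.85 / 2 = 94.35, taken as 94.

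**3. Chance imbalance in one AIS grade**

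The protocol gives no grade shares, so a share q of 0.3 to 0.6 is assumed. The standard error of the between-arm difference in share is √(2q(1−q)/n). This treats grade as unrelated to age and country.

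- n = 111, q = 0.3: SE = 0.062, 95% range ±12 points, P(10 points or more) = 10%.
- n = 111, q = 0.5: SE = 0.067, 95% range ±13 points, P = 14%.
- n = 94, q = 0.3: SE = 0.067, P = 13%.
- n = 94, q = 0.5: SE = 0.073, P = 17%.

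**4. What a 10-point imbalance does in a model without grade**

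Take a 50/50 split of grade A against B or C that explains a fraction R² of the variance (assumed). The gap between the two groups is 2√R² SD, so a 10-point imbalance shifts the arm difference by 0.1 × 2√R².

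- R² = 0.1: 0.06 SD.
- R² = 0.3: 0.11 SD.

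The standard error of the arm difference is √(2/94) = 0.146 SD. The shift is therefore about 0.4 to 0.75 of a standard error.

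**5. Power gained by adjusting**

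Assume a 0.35 SD effect and 94 per arm at a single visit. Adjustment raises the standardised effect to 0.35/√(1−R²). Power is from the noncentral t distribution.

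| R² (assumed) | Effective effect | Power |
|---|---|---|
| 0 | 0.350 | 67% |
| 0.1 | 0.369 | 71% |
| 0.2 | 0.391 | 76% |
| 0.3 | 0.418 | 81% |

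**6. The primary model, for comparison**

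In 20,000 simulated draws of grade counts with 94 per arm, lack of balance on grade inflated the variance of the grade-adjusted treatment effect by a mean factor of 1.011 (95th percentile 1.033). Power was 85.1% against 85.5% with perfect balance at R² = 0, and 91.8% against 92.1% at R² = 0.2. Leaving grade out of the minimisation costs the primary analysis 0.3 to 0.4 power points.

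**The case against.** The strongest reply is that 10.3 calls itself a brief summary and defers the detail to a SAP, which is not shown. A SAP may add covariates. In addition, the word baseline in the logistic sentence is undefined and could include AIS grade. Minimising on few factors and adjusting for severity in the analysis is a legitimate design, and 10.3.1 will show baseline outcome measures by arm, so an imbalance would be visible. Chance imbalance is also already reflected in the confidence interval and is not bias.

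Most of this stands and limits the point. It does not remove it, because 10.3.3 does not merely stay silent: it fixes a covariate list for HRQoL, and that list contains a term that the schedule cannot supply. For the logistic models the point is weaker and amounts to asking for an explicit name.

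A reader might infer more from these passages. The documents do not support the following:

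- *That AIS grade is the only prognostic factor in the primary model.* Age group is named there too.
- *That severity is excluded from the subgroups.* Section 10.4 says "Exploratory sub-group analyses will assess the impact of the minimisation factors under the treatment effect", but its next sentence leaves the planned subgroups to the SAP.
- *That all secondary outcomes lack severity adjustment.* The regressions for other continuous outcomes allow further prognostic factors.
- *That the survival model should carry AIS grade.* Section 10.1 expects 2–3% mortality by 6 months, which is about 4 to 7 deaths in 222 (222 × 0.02 = 4.4; 222 × 0.03 = 6.7). Deaths at 12 months are not stated. Extra covariates on so few events may give an unstable fit.
- *That the minimisation must be changed now.* Version 10.0 of December 2025 extends a recruitment already under way, and the gain in the primary model would be the 0.3 to 0.4 power points above. The gain from 67% to 71–81% comes from adjustment, not from minimising.

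**Conclusion.** The point holds as a small, inexpensive improvement. AIS grade is not balanced by design. It is not named in the HRQoL and logistic models of 10.3.3, and the HRQoL model as written has no severity adjustment because no baseline SF-36 exists.

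The benefit is precision and protection against a chance imbalance: about 4 to 15 power points for a 0.35 SD effect. That range depends on the assumed R² of 10 to 30%, the assumed effect size and 94 evaluable per arm. None of the documents gives an R² or the AIS mix. No systematic bias is shown, and the primary analysis is not at risk.

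**What to change.** In 10.3.3:

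- **HRQoL mixed model:** replace the baseline score with baseline AIS grade (A, B, C) as a fixed effect, matching the primary model. The same section plans graphs of HRQoL change from baseline; replace these with values at 6 and 12 months, since no change can be computed.
- **Logistic models:** name baseline AIS grade as a covariate where the number of events allows, and say what baseline means for each binary outcome.

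Carry the same wording into the SAP before unblinding. The cost is a short text amendment and two further model parameters (three grades). AIS grade is already recorded for every participant as an eligibility item, so no data collection, sample size or randomisation system changes.
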